#### 9.7.1.8.3 LABORATORY VALUES

Laboratory results will be summarized using Système International (SI) units, as appropriate. For all quantitative parameters listed in [Section 9.5.1.4.3](#), the actual value and the change from baseline to each postbaseline visit and to the end of treatment (defined as the last on-treatment value) will be summarized by visit and treatment group using descriptive statistics. Qualitative parameters listed in [Section 9.5.1.4.3](#) will be summarized using frequencies (number and percentage of subjects), and changes from baseline to each postbaseline visit and to end of treatment will be reported using shift tables. Percentages will be based on the number of subjects with both nonmissing baseline and relevant postbaseline results.

Laboratory test results will be assigned a low/normal/high (LNH) classification according to whether the value was below (L), within (N), or above (H) the laboratory parameter's reference range. Within-treatment comparisons for each laboratory parameter will be based on shift tables that compare the baseline LNH classification to the LNH classification at each postbaseline visit and at the end of treatment. Similar shift tables will also compare the baseline LNH classification to the LNH classification for the highest and lowest value during the treatment period.

#### 9.7.1.8.4 VITAL SIGNS

Descriptive statistics for vital signs parameters (ie, systolic and diastolic BP, pulse, respiratory rate, temperature, weight, and height) and changes from baseline will be presented by visit and treatment group.

Percentiles for BP values (only for subjects <18 years old) will also be summarized using a shift table of worst postbaseline from Baseline measurement by categories (<90th percentile, 90th to 95th percentile, 95th to  $\leq$ 99th percentile, systolic BP or diastolic BP >99th percentile). See [Appendix 5](#) and [Appendix 6](#) for detail on percentiles.

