## 9 INVESTIGATIONAL PLAN

### 9.1 Overall Study Design and Plan

This is a multicenter, randomized, open-label, parallel-group, Phase 2 study to compare the efficacy and safety of lenvatinib in combination with ifosfamide and etoposide versus ifosfamide and etoposide in children, adolescents, and young adults with relapsed or refractory osteosarcoma.

Approximately 72 eligible subjects will be randomized to 1 of the following 2 treatment arms in a 1:1 ratio within the strata:

- Arm A: lenvatinib 14 mg/m^2 (orally, once daily) plus ifosfamide 3000 mg/m^2/day (intravenously [IV], Day 1 to Day 3 of each cycle for a total of up to 5 cycles) and etoposide 100 mg/m^2/day (IV, Day 1 to Day 3 of each cycle for a total of up to 5 cycles)
- Arm B: ifosfamide 3000 mg/m^2/day (IV, Day 1 to Day 3 of each cycle for a total of up to 5 cycles) and etoposide 100 mg/m^2/day (IV, Day 1 to Day 3 of each cycle for a total of up to 5 cycles)

[figure not shown]
Randomization will follow a predefined randomization scheme based on the following stratification factors: time to first relapse/refractory disease (early [<18 months] or late [ $\geq$ 18 months]) and age (<18 and  $\geq$ 18 years).

The Sponsor will closely monitor enrollment, to ensure that a minimum of 36 subjects are <17 years of age at the time of informed consent.

The study will be conducted in 3 Phases: a Pre-randomization Phase, a Randomization Phase, and an Extension Phase.

The end of the study will be the date of data cutoff for the final analysis or the time of last subject last visit, whichever occurs later.

An overview of the overall study design is presented in [Figure 1](#).

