#### 9.1.2.1 Treatment Period

The Treatment Period for each subject will begin at the time of randomization and will end at the completion of the Off-Treatment Visit which will occur within 30 days after the final dose of study treatment.

Subjects will receive study treatment as continuous 21-day cycles in both treatment arms. Treatment cycles will be counted continuously regardless of dose interruptions. If chemotherapy administration is precluded on Day 1 of a treatment cycle, the subject may resume treatment once recovered at the discretion of investigator. Subsequent chemotherapy will be administered every 21 ( $\pm 1$ ) days starting from the timepoint it was resumed. Subjects will undergo safety and efficacy assessments as defined in the Schedule of Procedures/Assessments ([Table 5](#)). Subjects randomized to Arm A will continue to receive lenvatinib until disease progression (PD) confirmed by IIR, development of unacceptable toxicity, subject request, withdrawal of consent, or study termination by the sponsor, whichever occurs first.

Disease progression (PD) must be confirmed by IIR prior to the investigator discontinuing study treatment for a subject. In situations where the investigator judges that alternative treatments must be instituted immediately for a subject's safety, study drugs may be discontinued without waiting for IIR confirmation of radiographic evidence of PD. If possible, before discontinuation of the subject from the study, the investigator should consult with the sponsor.

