## **Dental Examination**

Information from studies in animals suggest that there is a risk of delayed tooth formation and/or physical growth and development. Therefore, dental examinations will be performed to evaluate subjects for potential anomalies in tooth formation and eruption schedule.

Dental examination by a qualified healthcare professional should be conducted per local institutional guidelines at baseline (C1D1  $\pm$  4 weeks), and thereafter per local standard of care (but no less than annually), and as part of the Off-treatment assessment. If the most recent dental examination is within 6 months prior to the Off-Treatment visit, the dental examination is not required. Post-baseline dental examinations are not required for subjects for whom permanent teeth (excluding third molars) are evaluated to be fully erupted at baseline.

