**Table 5 Schedule of Assessments in Study E7080-G000-230 – Randomization Phase**

Phase	Prerandomization		Randomization a (All cycles are 21 days in duration)																	
	Screening b	Baseline c	Treatment d																Off-Tx	Follow-up
Period	1	2	3	4	5	6	7	8	9	10	11	12	13	14	15	16	17	18+		
Visit	1	2	3	4	5	6	7	8	9	10	11	12	13	14	15	16	17	18+		
Cycle			Cycle 1			Cycle 2			Cycle 3			Cycle 4			Cycle 5			Cycle 6-X		
Day	-28 to -2	-1	1	8	15	1	8	15	1	8	15	1	8	15	1	8	15	1		
Procedures/Assessments																				

- o. Subjects randomized to Arm A will continue to receive lenvatinib only after completion of 5 cycles with lenvatinib+ifosfamide+etoposide until progressive disease, unacceptable toxicity, subject request, study termination by the sponsor, subject noncompliance with safety or efficacy assessments, or withdrawal of consent. Subjects randomized to Arm B will be off-treatment after 5 cycles of ifosfamide+etoposide.
- p. All subjects who receive suspension formulation, with the exception of subjects using a nasogastric or gastrostomy tube, must complete the Palatability Questionnaire on C1D1 (or the subsequent visit). If the subject is unable to complete the questionnaire this must be done by their parents or their legal guardian.
- q. **Screening:** Tumor assessments of the chest, abdomen, pelvis, and other areas of known disease or newly suspected disease should be performed within 28 days prior to C1D1. Scans of the abdomen, pelvis, and other areas of the body may be done with MRI instead of CT, but evaluation of the chest should be done with CT. CT scans should be performed with iodinated IV contrast and MRI scans should be performed with IV gadolinium chelate.

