- Treatment Phase:** Tumor assessments of the chest, and other areas of known disease at Screening or newly suspected disease should be performed every 6±1 weeks from the date of randomization until Week 18±1 week, then every 9±1 weeks until Week 54±1 week, and thereafter, every 12±2 weeks until documentation of PD during the Treatment Phase (or sooner if there is evidence of progressive disease) and should utilize the same methodology (CT or MRI) and scan acquisition techniques (including use or nonuse of IV contrast) as was used for the screening assessments. Tumor response will be assessed according to RECIST 1.1. Any CR or PR must be confirmed not less than 4 weeks following the initial achievement of the response. **Off-Treatment:** Tumor assessments at the Off-Treatment Visit (within 1 week of the Off-treatment Visit) are only necessary for subjects who discontinue study treatment without disease progression, if more than 4 weeks have passed since the previous assessment and if the subject will not continue with follow-up scans.
- Follow-up:** For subjects who discontinue study treatment without disease progression, tumor assessments should continue to be performed according to the schedule: every 6±1 weeks until Week 18±1 week, then every 9±1 weeks until Week 54±1 week, thereafter, to be performed every 12±2 weeks, until documentation of progression or start of a new anticancer agent.
- r. Brain CT with contrast or MRI pre- and post- gadolinium contrast will be performed at the Screening Visit as clinically indicated, and thereafter during treatment as clinically indicated. For subjects with protocol-eligible treated brain metastases, brain CT/MRI will be performed at all tumor assessment time points.
- s. Height will be assessed at the Baseline Visit, Day 1 of every 4 cycles during the Treatment Phase, at the Off-treatment Visit and every 3 months during the Post-treatment Follow-up. Assessment of height in Post-treatment Follow-up is not required once pubertal development is complete. Proximal tibial growth plate x-rays should be conducted for subjects aged <18 years at baseline and at the Off-treatment Visit. If the growth plates are closed at baseline

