### 9.7.1.8 Safety Analyses

All safety analyses will be performed on the Safety Analysis Set. Safety data, presented by treatment group, will be summarized on an “as treated” basis using descriptive statistics (eg, n, mean, standard deviation, median, minimum, maximum for continuous variables; n [%] for categorical variables), as appropriate. Safety variables include TEAEs, clinical laboratory parameters, vital signs, 12-lead ECG results, Lansky play scores or Karnofsky performance scores, physical examination, height, tooth formation abnormalities, closure of proximal tibial plates, and LVEF. Study Day 1 for all safety analyses will be defined as the date of the first dose of study drug.

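### The Off-treatment height summary compares centimetres gained over a longer time in Arm A than in Arm B, so it can mask slowed growth

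*Protocol*

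**What the plan says.** The protocol gives growth as a safety concern. The dental examination paragraph of Section 9.5.1.4.7 states: "Information from studies in animals suggest that there is a risk of delayed tooth formation and/or physical growth and development". Section 9.7.1.8 then lists the safety variables, among them "physical examination, height, tooth formation abnormalities, closure of proximal tibial plates, and LVEF".

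The height summary itself is in Section 9.7.1.8.4. Height is one of the vital signs, for which values "respiratory rate, temperature, weight, and height) and changes from baseline will be presented by visit and treatment group". The same section adds age-based percentiles for blood pressure in subjects under 18, but gives no percentile, z-score or velocity for height.

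The timing of the heights comes from elsewhere:
- Table 5, footnote s: baseline, Day 1 of every four cycles, then "at the Off-treatment Visit and every 3 months during the Post-treatment Follow-up". A waiver follows: "Assessment of height in Post-treatment Follow-up is not required once pubertal development is complete".
- Section 9.1.2.1: the Treatment Period ends with "the Off-Treatment Visit which will occur within 30 days after the final dose of study treatment". Arm A stays on lenvatinib until confirmed progression or another stopping reason.
- Table 5, footnote o: "Subjects randomized to Arm B will be off-treatment after 5 cycles of ifosfamide+etoposide".

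**The concern.** In a growing child, height gained depends mainly on how much time has passed. A by-visit table is fair only if a visit falls at the same elapsed time in both arms. The Off-Treatment Visit does not: it follows the last dose, and the design makes the last dose later in Arm A.

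The direction is the unhelpful one. The extra months add centimetres to the arm that receives the drug under suspicion. A moderate slowing of growth under lenvatinib could leave Arm A with the larger mean gain, and a reader of that row would see no sign of a problem.

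**Working it through.** **Design inputs.** The protocol gives no figure for height over time, so the calculation starts from its PFS assumptions (Section 9.7.2): medians of 8.75 months (Arm A) and 3.5 months (Arm B). These agree with the stated hazard ratio, 3.5/8.75 = 0.4, and with the stated number of events: 4 × (1.960 + 0.842)² / (ln 0.4)² = 37.4, rounded up to 38.

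**Other inputs.**
- From the protocol: 21-day cycles; chemotherapy on Days 1 to 3 for at most five cycles; 20 months of enrolment; primary analysis at about month 32; 25.8% stopping for adverse events on the combination in Study 207 (Section 7.3.1).
- Assumed: exponential times; uniform accrual; 40% toxicity stops as an alternative; a month-24 cutoff as an alternative; chemotherapy delayed by 0 or 6 weeks; the Off-Treatment Visit 0, 15 or 30 days after the last dose.

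**Arm B, mean time to the Off-treatment height.** The last dose is at the latest on day 4 × 21 + 3 = 87, or day 129 with a 6-week delay. With λ = ln 2/3.5 = 0.198 per month, cap c, and 30.44 days per month, the mean is (1 − e^(−λc))/λ plus the lag.
- c = 87 days (2.86 months): 2.18 + 0.49 = 2.68 months.
- c = 129 days (4.24 months): 2.87 + 0.49 = 3.36 months.

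**Arm A.** Progression hazard is ln 2/8.75 = 0.0792 per month. Toxicity is a competing hazard of 0.0792 × p/(1 − p): 0.0275 for p = 25.8% and 0.0528 for p = 40%. A subject counts if the Off-Treatment Visit falls before the cutoff. The means were obtained by simulation.

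**Break-even.** At constant velocity, and with growth slowed by a fraction s in Arm A, the raw gains are equal when (1 − s) × A = B, so s = 1 − B/A. The growth rate cancels. With the visit 15 days after stopping:

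| Toxicity stops | Cutoff (month) | Arm A mean (months) | s, Arm B cap day 87 | s, Arm B cap day 129 |
|---|---|---|---|---|
| 25.8% | 24 | 5.82 | 54% | 42% |
| 25.8% | 32 | 7.36 | 64% | 54% |
| 40% | 24 | 5.36 | 50% | 37% |
| 40% | 32 | 6.61 | 59% | 49% |

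With the visit on the day of stopping, s runs from 42% to 69%. With the visit 30 days later, it runs from 33% to 59%. The overall range is 33% to 69%.

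**Illustration.** The documents give no size for any lenvatinib effect on growth. If it were a 30% slowing, Arm A's raw gain at the 15-day lag would be about 0.7 × 5.36/3.36 = 1.1 to 0.7 × 7.36/2.68 = 1.9 times Arm B's.

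**The time-matched height.** Read as Cycles 1, 5, 9 and so on, the four-cycle schedule puts the last on-treatment height shared by both arms at Cycle 5 Day 1, week 12. That comparison is not distorted by elapsed time. It is short, and subjects who have finished growing dilute it: the enrolment rule is only that "a minimum of 36 subjects are <17 years of age at the time of informed consent", so up to 36 of about 72 may be 17 or older.

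**The case against.** The strongest reply is that this belongs to the SAP. Sections 9.7 and 9.7.1 defer detail to a plan that is not shown, and a z-score or velocity table is ordinary content for it. Section 9.7.1.8.4 gives one sentence for all vital signs, sets no Off-treatment contrast or test, and does not say that height will be shown in no other way. That limits the point: a reader might infer that the trial will never standardise height, and the documents do not support that. But the protocol does state a summary, Off-treatment is one of its height visits, and the summary misleads there.

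A second reply is that growth is watched in other ways: growth-plate x-rays, Tanner stage, dental examinations and three-monthly follow-up heights, with exposure summarised under Section 9.7.1.8.1. A reader who checks exposure can partly see the imbalance. It would be wrong to say that the trial ignores growth. None of these, however, corrects the height row.

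Three further objections stand and shape the conclusion:
- **Crossover.** Arm B subjects who progress may start lenvatinib within 30 days (Section 9.1.4), with their own height schedule (Table 7). The first follow-up height falls about 5.7 to 6.4 months from the start in Arm B. Under the design median, 1 − e^(−0.198 × 5.7) to 1 − e^(−0.198 × 6.4), or about 68% to 72%, would have progressed by then. Uptake is unknown, so Arm B follow-up heights cannot be treated as free of lenvatinib, and no break-even figure is offered for them.
- **Constant velocity.** The ratios need no growth rate, but they do need velocity that is constant over time, the same in both arms apart from lenvatinib, and unrelated to time on treatment.
- **Amputation.** Section 9.4.1 anticipates amputees when it discusses body surface area. Reference percentiles can mislead in such subjects.

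**Conclusion.** The point holds for one descriptive row. As stated, the Off-treatment height change compares about 2.7 to 3.4 months of growth in Arm B with about 5.4 to 7.4 months in Arm A (visit 15 days after stopping). Arm A would show more raw growth unless lenvatinib slowed it by more than roughly 33% to 69%, the range across visit lags of 0 to 30 days. The size is illustrative: it rests on exponential times at the design medians, the assumed toxicity stops, cutoffs and delays, and the constant-velocity conditions above. The direction follows from the visit definition and the longer treatment planned in Arm A.

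A reader might infer that every height comparison is biased, or that a growth harm is being concealed. Neither follows. The Cycle 5 Day 1 height is time-matched, no test rests on the Off-treatment row, the growth risk is an animal finding, and the primary analysis is untouched. This is a minor point about a descriptive safety table and a cheap improvement.

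**What to change.** Add to Section 9.7.1.8.4:
- For subjects under 18 or with open growth plates at baseline, also summarise height as an age- and sex-standardised z-score or percentile, or as height velocity, with change from baseline, by treatment group and time since first dose.
- Leave Arm B heights taken after the start of crossover lenvatinib out of the Arm B summary, or show them separately.
- Flag or exclude subjects whose measured height is affected by lower-limb amputation or surgery.
- Do not interpret the raw Off-treatment height change between arms without elapsed time.

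The cost is one derived variable and one table. Height, sex, date of birth (or age) and visit dates are already collected. The blood pressure tables in Appendices 5 and 6 are read by height percentile, so that percentile is already needed for subjects under 18. No new assessment is required.

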#### 9.7.1.8.5 ELECTROCARDIOGRAMS

Descriptive statistics for electrocardiogram parameters (HR, PR, QRS, QT, QTcB, QTcF and RR) and changes from Baseline will be presented by visit. Electrocardiogram (ECG) findings will be summarized. A shift table of worst postbaseline values from Baseline for ECG findings will be provided.

QTc Bazett and QTc Fridericia will be summarized. QTc Bazett and QTc Fridericia will be categorized as both maximum increases from Baseline and maximum postbaseline values.

#### 9.7.1.8.6 OTHER SAFETY ANALYSES

Descriptive summary statistics for LVEF changes from baseline will be calculated and summarized.

The shift of worst postbaseline proteinuria from Baseline will be summarized.

Thyroid-stimulating hormone values will be summarized in 2 categories ( $\leq$ ULN and >ULN).

Lansky play scores or Karnofsky Performance Status score scores will be summarized by shifts from Baseline to worst postbaseline visit.

Radiographic findings of proximal tibial growth plates will be listed and analyzed if appropriate.

Tooth formation abnormalities will be listed and analyzed if appropriate.

#### 9.7.1.9 Other Analyses

##### 9.7.1.9.1 HEALTH-RELATED QUALITY OF LIFE

Descriptive statistics will be presented for all PedsQL endpoints at each analysis time period by treatment arm. Baseline is defined as the later value of Day -1 or at Cycle 1 Day 1 prior to treatment.

This will be collected at baseline, at C2D1, C3D1, Week 18, C8D1, C18 D1 and at the Off-Treatment Visit. Score change from baseline in PedsQL at each analysis timepoint will be analyzed. Primary timepoint for assessment is at week 18 for all PedsQL endpoints.

Detailed HRQoL analysis plan will be provided in a separate analysis plan and the results will be provided in a stand-alone report.

#### 9.7.1.9.2 PALATABILITY AND ACCEPTABILITY QUESTIONNAIRE

Measurement of palatability will be assessed using a facial Hedonic scale ([Guinard, 2001](#)), in subjects receiving the suspension formulation in the study.

#### 9.7.2 Determination of Sample Size

A total sample size of 72 subjects is estimated for the primary efficacy endpoint of PFS. A median PFS of 3.5 months for Arm B (control arm) has been estimated by comparing available PFS data from clinically active agents in this patient population ([Davis, et al., 2019](#); [Palmerini, et al, 2016](#); [Grignani, et al., 2012](#)). With respect to Arm A (lenvatinib plus chemotherapy arm), a median PFS of 8.75 months is estimated based on the results from Study 207.

Therefore, assuming a hazard ratio of 0.4, a 1-sided type 1 error rate of 0.025, and power of 80%, the required number of PFS events for the study is 38. The primary PFS analysis is estimated to occur at approximately 32 months after the first subject is randomized (assuming a 20-month enrollment period), and accounts for a dropout rate of up to 40%.

#### 9.7.3 Interim Analysis

No interim analysis is planned for this study.

The safety monitoring will be conducted by the independent data monitoring committee (IDMC). The frequency of the safety reviews will be defined in the IDMC charter. Minutes from the open meetings of the IDMC will be provided if requested by regulatory agencies. The recommendation of whether to stop the study for safety will be reached by the IDMC based on their review of safety data with treatment information. The function and membership of the IDMC will be described in the IDMC charter.

#### 9.7.4 Other Statistical/Analytical Issues

Not applicable.

#### 9.7.5 Procedure for Revising the Statistical Analysis Plan

If the SAP needs to be revised after the study starts, the sponsor will determine how the revision impacts the study and how the revision should be implemented. The details of the revision will be documented and described in the clinical study report.

## **11 PROCEDURES AND INSTRUCTIONS (ADMINISTRATIVE PROCEDURES)**

### **11.1 Changes to the Protocol**

Any change to the protocol requires a written protocol amendment or administrative change that must be approved by the sponsor before implementation. Amendments specifically affecting the safety of subjects, the scope of the investigation, or the scientific quality of the study require submission to health or regulatory authorities as well as additional approval by the applicable IRBs/IECs. These requirements should in no way prevent any immediate action from being taken by the investigator, or by the sponsor, in the interest of preserving the safety of all subjects included in the study. If the investigator determines that an immediate change to or deviation from the protocol is necessary for safety reasons to eliminate an immediate hazard to the subjects, the sponsor's medical monitor and the IRB/IEC for the site must be notified immediately. The sponsor must notify the health or regulatory authority as required per local regulations.

Protocol amendments that affect only administrative aspects of the study may not require submission to health or regulatory authority or the IRB/IEC, but the health or regulatory authority and IRB/IEC (or if regionally required, the head of the medical institution) should be kept informed of such changes as required by local regulations. In these cases, the sponsor may be required to send a letter to the IRB/IEC and the Competent Authorities (or, if regionally required, the head of the medical institution) detailing such changes.

